### 16.2 Sample Size and Power Calculations

Power determination for the correlation analysis was carried out using the R-package pwr. This package

Figure 4 Power Determination

Sample size required to detect a positive correlation given various scenarios of r and beta values.

implements the power calculation methods described in Cohen, 1988. Assuming r is >0.78, a sample size of 10 women achieves 80% power (Figure 2). This assumed r value is more conservative than our previous observation of TFV concentration in rectal fluid versus tissue homogenate where r was 0.944.

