## 5. Protocol Summary

Protocol Chair:	[name], MS
Sample Size:	10 cisgender females
Study Population:	Premenopausal healthy volunteer cisgender women between 18-49 years of age with an intact gastrointestinal tract
Study Site(s):	NC TraCS Clinical Translational Research Center at the University of North Carolina, Chapel Hill, NC USA
Study Design:	Single-center, open-label PK sampling study
Study Duration:	Women will be enrolled in the study within 42 days of screening, depending on the timing of their menstrual cycle, and then will be on active study for two weeks. A follow-up visit will occur within 14 days.
Study Products:	Truvada®
Study Regimen:	Five witnessed doses daily prior to each sampling visit
Primary Objectives:	To assess the impact of high and low in vivo estradiol exposure on PrEP nucleotide concentrations in different cellular populations of the lower GI tract
Hypothesis:	PrEP nucleotide concentrations in total rectal cells collected via cytobrush will significantly correlate with concentrations in CD4 + T cells isolated from rectal tissue biopsies regardless of in vivo estradiol exposure.
Secondary Objectives:	
To quantify the relationship between estradiol, progesterone and testosterone on PrEP nucleotide concentrations in rectal and peripheral blood mononuclear cells
 
To quantify the relationship between estradiol, progesterone and testosterone on PrEP concentrations in plasma

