### 16.1 Statistical analysis.

*We hypothesize that PrEP nucleotide concentrations in total rectal cells obtained via cytobrush will significantly correlate with isolated CD4+ T cells regardless of estradiol exposure.* To test this hypothesis TFVdp and dATP concentrations in total rectal cells collected by cytobrush at each visit will be compared to CD4+ T cells isolated from rectal biopsies using Pearson's correlation. We expect strong correlations ( $>0.8$ ) to exist during both visits. Linear regression will be performed for log10 concentrations of total rectal cells (X) vs isolated CD4+ T cells (Y) to describe the relationship between these sampling matrices within each visit. These analyses will also be performed for FTCtp and dCTP.

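### The 80% power in section 16.2 is for one correlation at one visit; if the section 16.1 hypothesis needs significance at both visits, power at r = 0.78 is about 67% to 77%

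*Combined protocol and SAP*

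**What the plan says.** Section 16.1 and the Protocol Summary (section 5) state the hypothesis. Nucleotide concentrations in total rectal cells "collected via cytobrush will significantly correlate with concentrations in" CD4+ T cells from biopsies, and section 16.1 words it as "significantly correlate with isolated CD4+ T cells regardless of estradiol exposure". Exposure is varied by visit: section 10.1 places Visit 1 where estradiol is predicted to be lowest and Visit 2 where it is predicted to be highest.

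The test in section 16.1 is a Pearson correlation. TFVdp and dATP in cells "collected by cytobrush at each visit will be compared to CD4+ T cells isolated from rectal biopsies", and the same is done for FTCtp and dCTP. Correlations above 0.8 are expected "to exist during both visits". Linear regression is added "to describe the relationship between these sampling matrices within each visit". The plan has no test that pools the visits and no test of a difference between them.

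Section 16.2 gives one power figure. "Power determination for the correlation analysis was carried out using the R-package pwr", and for r above 0.78 "a sample size of 10 women achieves 80% power". The caption of Figure 4 reads "Sample size required to detect a positive correlation given various scenarios of r and beta values". The section's text names no visit, nucleotide, alpha or sidedness. Figure 4 itself is not reproduced in the text available, so it may give the last two.

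**The concern.** A reader who goes from section 16.1 to section 16.2 will take 80% as the chance that the study supports its hypothesis when the true correlation is 0.78. The calculation covers one correlation, while the hypothesis concerns two exposure conditions, each with its own test in the same 10 women. A significant result at one visit only would not show a correlation that holds regardless of exposure. If both must be significant, the relevant power is a joint probability. That can be no higher than the single-test power and is lower unless the two tests nearly always agree.

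At stake is how a failure would be read. At the planning value, the chance that one nucleotide misses significance at one or both visits may be well above what the 80% suggests. A miss could then be taken as an effect of estradiol on the surrogate relationship when it is only sampling error.

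**Working it through.** **Inputs.** n = 10 evaluable women, unevaluable participants replaced (16.3); r = 0.78, the lower bound of the assumption (16.2); one Pearson test at each of two visits (16.1). Assumed: alpha 0.05 two-sided, because the text does not give it, and a range of between-visit correlations, because the documents give none.

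**Step 1: reproduce the 80%.** The pwr formula for a correlation uses

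- critical r: r_c = √[t² / (t² + n − 2)], with t = 2.306 on 8 df, so r_c = 0.632
- z_r = atanh(r) + r / [2(n − 1)] = 1.0454 + 0.78/18 = 1.0887
- z_c = atanh(0.632) = 0.7446
- power = Φ[(z_r − z_c) × √(n − 3)] = Φ[0.3441 × 2.6458] = Φ(0.910) = 81.9% (the opposite tail is negligible)

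Solving for n at 80% power gives 9.65, which rounds up to 10. The stated figure therefore reproduces as one two-sided 5% test. A one-sided 5% test needs only n = 8.03 and has 89.4% power at n = 10, which does not fit. Direct simulation of the t test gives 83.4% for the same single test, slightly above the pwr approximation.

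**Step 2: both visits, independent.** Joint power is the square of the single-test power.

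- pwr formula: 0.8187² = 67.0%
- simulation: 69.6%

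**Step 3: both visits, dependent.** Simulation of bivariate normal data, n = 10, r = 0.78 at each visit, two-sided 5%, 600,000 runs per setting. Each matrix correlates ρ with itself between visits, and the correlation of one matrix at one visit with the other matrix at the other visit is r × ρ.

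| ρ (assumed) | Significant at both visits |
|---|---|
| 0 | 69.6% |
| 0.3 | 70.2% |
| 0.5 | 71.2% |
| 0.7 | 73.2% |
| 0.9 | 77.0% |
| 0.95 | 78.9% |
| 0.98 | 80.5% |
| 0.99 | 81.3% |

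The cross-visit, cross-matrix term matters too. At ρ = 0.9 it is 0.78 × 0.9 = 0.70 in the table; setting it to 0.78 instead lowers 77% to 75%. At ρ = 0.5, values of that term from 0.3 to 0.7 give 70.6% to 74.3%.

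**Step 4: how far the gap extends.** Both-visits power at n = 10:

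| r | pwr, independent | Simulation, ρ = 0 | Simulation, ρ = 0.9 |
|---|---|---|---|
| 0.78 | 67.0% | 69.6% | 77.0% |
| 0.80 | 0.8541² = 73.0% | 75.6% | 81.4% |
| 0.85 | 0.9304² = 86.6% | 88.4% | 90.9% |

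Under independence, 80% at both visits is reached at r of about 0.816 by simulation and 0.825 by the pwr formula. At the prior r of 0.944 cited in section 16.2, the pwr formula gives 99.6%.

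**The case against.** Several points on the other side are sound.

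- **The stated figure is not wrong.** A reader might infer that section 16.2 contains an arithmetic error. It does not: the 80% reproduces, and the singular wording of the Figure 4 caption fits a single-correlation calculation.
- **The both-visits rule is inferred.** The plan attaches no pass/fail decision to the correlations. In a 10-woman sampling study, reporting two visit-specific correlations, each with its own power, is a legitimate aim, and the joint power figures exist only under the both-visits rule. This stands, and it is why the fix asks for the rule to be stated. It does not remove the point, because a claim that holds regardless of exposure is hard to support from one visit alone.
- **The gap sits at the edge of the assumption.** Section 16.2 says r is above 0.78 and section 16.1 expects above 0.8. At r = 0.85 the shortfall is gone. This also stands and limits the size of the point. Still, 0.78 is the value on which the power statement rests, and the 0.944 comes from parent TFV in rectal fluid against homogenate, a different analyte in different matrices.
- **Independence is unlikely in the same women.** Agreed, but at r = 0.78 joint power stays below 80% up to ρ = 0.95.
- **Alpha and sidedness may be in Figure 4.** They cannot be called missing from the plan. If the test were one-sided at 5%, both-visits power under independence would be 0.8938² = 79.9% by pwr, or 82.1% by simulation, and the shortfall would all but vanish. The stated sample size of 10 would then not follow from the calculation, however.

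**Conclusion.** The 80% is correct for one nucleotide at one visit but is not the power for the hypothesis in section 16.1, if that hypothesis requires significance at both visits. At r = 0.78 and n = 10, the chance of missing significance at one or both visits is about 30% with independent visits (100 − 69.6) and 23% at ρ = 0.9 (100 − 77.0), against 17% for a single test (100 − 83.4), all by simulation.

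This rests on a two-sided 5% level, inferred because it reproduces the stated figure; on bivariate normality; on one nucleotide; and on dependence values that are assumptions. If both TFVdp and dATP had to succeed at both visits, power could be lower again; that was not calculated.

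A reader might go further and conclude that 10 women are too few. The documents do not support that. Under independence, 12 women would give about 82% at r = 0.78 by simulation, but the plan expects r above 0.8, and at about 0.82 the planned 10 already give 80% at both visits. The point concerns what the power statement claims, not whether the study should be larger.

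**What to change.** Change the text of section 16.2 only.

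1. Label the 80% as power for one nucleotide at one visit.
2. State in one sentence whether the hypothesis requires significance at both visits.
3. If it does, restate the power and name the method and the dependence. For example: *For one nucleotide to be significant at both visits (n = 10, r = 0.78, two-sided 5%), power is about 67% (pwr formula) to 70% (simulation) if visits are independent, about 71% at an assumed between-visit correlation of 0.5, and about 75% to 77% at 0.9, depending on the correlation between matrices across visits.* Alternatively, state that r of about 0.82 at each visit is needed for 80% under independence.
4. If another rule is intended, or if both TFVdp and dATP must succeed, state that rule and its power instead.
5. Confirm alpha and sidedness in the text if Figure 4 does not already give them.

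Sample size and analysis do not change. The only cost is a less favourable stated power for the hypothesis.

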### 16.3 Participant Accrual, Follow-up and Retention

A total of 10 evaluable women will be enrolled over a period of approximately 5 months. Participants who complete all visits but the follow-up visit will still be considered evaluable. All unevaluable participants will be replaced.

## 17. Data and Safety Monitoring and Analysis

### 17.1 Clinical Data Monitoring

The study physician will meet with the PA for screen and entry reviews. The key indicators that will be assessed include informed consents, eligibility criteria, drug dosing, protocol required evaluations, review of subject responsibilities, and contraception counseling. Additionally, laboratory results, concomitant medications, proper error documentation, adherence to unit specific SOPs, and CRF completion will be assessed. When meeting for “on-study” reviews, the key indicators that will be assessed are SAE reporting, adverse event monitoring, and implementation of new protocol versions and amendments. Additionally, missed visits, proper symptom grading, laboratory results, concomitant medications, proper error documentation, adherence to unit specific SOPs, and CRF completion will be reassessed. Additional training on source documentation and good clinical practices will be addressed as needed.

### 17.2 Sample and Data Analysis

All blood, cells, and rectal tissue samples will be analyzed by the Clinical Pharmacology and Analytical Chemistry Laboratory (CPAC) at the UNC School of Pharmacy, which is directed by [name]. TFV and FTC will be quantified in plasma by validated LC-MS/MS methods (lower limit of quantification; LLOQ=1ng/ml). TFVdp, FTCtp, dATP and dCTP will be quantified in PBMCs and rectal cell lysates by validated LC-MS/MS methods (LLOQ=0.02ng/ml). These analyses will be performed at the UNC CFAR Clinical Pharmacology and Analytical Chemistry Core (see [name] letter).

## 18. Data Handling and Record Keeping

### 18.1 Data Management Responsibilities

The investigator will maintain, and store securely, complete, accurate and current study records throughout the study. The investigator will retain all study records for at least three years following the completion of the study. Study records must be maintained on site for the entire period of study implementation.

### 18.2 Quality Control and Quality Assurance

The quality control and assurance of clinical study data will be the responsibility of the study physician assistant, [name]. All clinical charts prepared by study staff will be reviewed by [name] for quality assurance within 7 days of the subject visit. Quality assurance for analytical methods and drug concentration data will be performed by the quality control officer [name].

### 18.3 Study Coordination

The coordination of subject visits will be the responsibility of the clinical team, led by the study Physician Assistant.

## 19. Clinical Site Monitoring

All clinical and experimental activities related to this study will be conducted at the University of North Carolina at Chapel Hill. There will be no enrollment outside this institution. The investigators listed in the team roster have affiliations with UNC Eshelman School of Pharmacy and UNC School of Medicine/Center of Infectious Disease. Site quality management will be the responsibility of the principal investigator and co-investigators, and this process will follow the guidelines and operating policies already established by the UNC ACTU. The Clinical Pharmacology and Analytical Chemistry Core (CPAC) and its Director, will provide oversight for laboratory personnel who are not governed by the ACTU policies.

The principal investigator will hold weekly meetings to discuss clinical research and laboratory activities. Concerns in these matters will be addressed during these meetings.

### 19.1 Human Participants Protection

The investigators will make efforts to minimize risks to participants. Volunteers and study staff members will take part in a thorough informed consent process. Before beginning the study, the investigators will have obtained IRB approval and the protocol will have been submitted to the FDA. The investigators will permit audits by the FDA or any of their appointed agents.

### 19.2 Institutional Review Boards

The final protocol (version 1.0) will be submitted along with the informed consent to the UNC IRB. Modifications will be made to version 1.0 after initial review for final approval by the UNC IRB. Subsequent to initial review and approval, the IRB will review the protocol at least annually. The Investigator will make safety and progress reports to the IRB at least annually. These reports will include the total number of participants enrolled in the study, the number of participants who completed the

study, all changes in the research activity, and all unanticipated problems involving risks to human participants or others.

### 19.3 Risk Benefits Statement

This research study is designed to gain new knowledge for society. Participants participating in this research will not receive any direct benefit from their participation. Certain risks are associated with the study procedures and are listed below.

### 19.4 Risks

#### 1. **Blood Draws:**

Risks associated with blood draws include bleeding, discomfort, feelings of dizziness or faintness, and/or bruising, swelling and/or infection.

#### 2. **STI Screening/Reporting:**

Disclosure of STI status may cause sadness or depression in volunteers. Partner notification of STI status may cause problems in their relationships with their sexual partners. Additionally, participants could misunderstand the current experimental status of the study medication and as a result increase their HIV risk behaviors while in the study. The following STIs are required by law to be reported to the NC State Department of Health if positive: HIV, Syphilis, gonorrhea, Chlamydia, Hepatitis B and C.

#### 3. **Anoscopy with rectal biopsy and cells:**

This is a commonly practiced medical procedure and the procedures done in this trial will not involve any unusual risks or discomforts. The risks associated with these procedures include mild discomfort and the feeling of having a “bloated stomach.” Anoscopic biopsies are painless and heal quickly (usually within three days). On extremely rare occasions, the procedure or biopsies may lead to pain, infection (sepsis), bleeding or perforation of the

gastrointestinal tract. Perforation occurs approximately once out of every 100,000 procedures. If this extremely rare complication occurs, antibiotics and surgery to repair the perforation may be necessary.

**4. Confidentiality:**

Participation in clinical research includes the risks of loss of confidentiality and discomfort with personal nature of questions. Although the study site makes every effort to protect participant privacy and confidentiality, it is possible that participants' involvement in the study could become known to others, and that social harms may result.

**5. Study Drug:**

Truvada® tablets are fixed-dose combination tablets containing emtricitabine (FTC) 200mg and tenofovir disoproxil fumarate (TDF) 300mg in each tablet. There is some experience in healthy volunteers taking Truvada®. No new or unexpected side effects are observed with the fixed-dose tablet than those observed when each drug is given separately. The dosing regimens will be consistent with package insert recommendations. Individual daily doses of this magnitude were studied during development of both TDF and FTC and these were well tolerated. In our previous studies using the fixed-dose tablet in healthy volunteer research projects, there were no serious adverse events attributed to study drug.

FTC. The following side effects have been associated with the use of FTC: Headache, dizziness, tiredness, inability to sleep, unusual dreams, loose or watery stools, upset stomach (nausea) or vomiting, abdominal pain, rash, itching, skin darkening of the palms/soles, increased cough, runny nose, and abnormal liver function tests.

TDF. The most common side effects associated with oral TDF in patients with HIV infection are nausea, headache, diarrhea, vomiting, flatulence, asthenia, abdominal distension and anorexia. Less common side effects of TDF include kidney toxicities and low blood phosphate. Other side effects reported in the post-marketing period include weakness, pancreatitis, dizziness, shortness of breath, and rash. TDF has been associated with decreased bone mineral density in HIV-infected patients taking TDF tablets for 24-48 weeks.

## 19.5 Benefits

Participants in this study will experience no direct benefit. Participants and others may benefit in the future from information learned from this study. Specifically, information learned in this study may lead to the development of safe and effective interventions to prevent HIV transmission. Additionally, participants will be referred for treatment for any incidental findings detected during screening and other examinations.

## 19.6 Informed Consent Process

The investigators will obtain informed consent from each subject before starting any study procedures according to the standards set forth in the ICH Good Clinical Practice guidelines and per unit SOPs. The process will include reviewing consent forms with potential participants in a confidential setting and explaining all risks and benefits associated with participation of the study. This involves reading over the IRB-approved consent form with the subject in a private space, soliciting questions from the subject, allowing the subject ample time alone to review the form, soliciting questions again, and then offering the subject the opportunity to sign the consent form. To ensure understanding, study staff may ask questions of the participants regarding study procedures. The consent forms will use language that is sufficiently simple for lay persons to comprehend. Participants will not be coerced into participating. Children under the age of 18 years, decisionally impaired adults and

non-English speakers will not be enrolled in this study. Each subject will be provided with a photocopy of all documents that she signs. The informed consent process will cover all elements of informed consent required by research regulations. In addition, the process specifically will address the following topics of importance to this study:

1. The unknown safety and unproven efficacy of the study products
2. The need to practice safer sex behaviors regardless of study treatment group
3. The importance of adherence to the study visit and procedures schedule
4. The potential medical risks of study participation (and what to do if such risks are experienced)
5. The potential social harms associated with study participation (and what to do if such harms are experienced)
6. The real yet limited benefits of study participation
7. The distinction between research and clinical care
8. The right to withdraw from the study at any time

The informed consent process will include an assessment of each potential participant's understanding prior to enrollment and sequential assignment of concepts identified by the protocol team as essential to the informed consent decision.

Participants who are not able to demonstrate adequate understanding of key concepts after exhaustive educational efforts will not be enrolled in the study.

#### 19.7 Participation Confidentiality

Confidentiality will be maintained by storing all specimens for current and future use with a unique identifying number, which will be linked to the subject's name, social security number, address, telephone number, and hospital medical record (MR) number. The principal investigators and study staff will be the only people with

access to the identifying information. Any information provided to other people working on this study will be given with the study ID number, not other identifying information. The records will be secured in a locked file cabinet in the locked office specifically designated for study record storage purposes.

All electronic data for this study will be stored on a dedicated University server which contains extensive protections and securities. The server is housed and administered at the server farm at the Manning Data Center, located at [name].

#### 19.8 Special Populations

Children under the age of 18 years, decisionally impaired adults and non-English speakers will not be enrolled in this study.

